## 8.7 Clinical Evaluation

### 8.7.1 Analysis of Clinical Evaluation

The clinical endpoints evaluation will be conducted on the Safety population.

For all by-visit analyses of clinical endpoints, the final visit is either Week 12/Visit 6 if a subject completed the study, or the discontinuation visit.

#### PASI

The PASI will be analyzed for the following endpoints:

- Change from Baseline at Week 4, 8, and 12/EOT (the primary clinical efficacy endpoint)
- Proportion of subjects with PASI-50 (defined as a reduction of  $\geq 50\%$  from baseline) at Week 4, 8, and 12/EOT
- Proportion of subjects with PASI-75 (defined as a reduction of  $\geq 75\%$  from baseline) at Week 4, 8, and 12/EOT

#### IGA

The IGA will be analyzed for the following endpoints:

- Change from baseline at Week 4, 8, and 12/EOT (the key secondary clinical efficacy endpoint)

The proportion of subjects in three categories:  $\geq 1$  grade decrease,  $\geq 2$  grade decrease, IGA=0 or 1 and  $\geq 2$  grade decrease from baseline at Week 4, 8, and 12/EOT

#### BSA

The BSA will be analyzed for the following endpoint:

- Change from Baseline in BSA score at each study visit (Week 4, 8, and 12/EOT)

### **PGIC**

The PGIC will be analyzed for the following endpoint:

- PGIC score at each study visit (Week 4, 8, and 12/EOT)

#### **8.7.2      *Statistical / Analytical Issues***

##### **8.7.2.1      Analysis Visit Windows for Assigning Observed Data**

Clinical evaluation data will be assigned to analysis visits based on its nominal scheduled visit. Early termination visit will be assigned to analysis visits as defined in the visit window tables below. If the early termination visit occurs within the same analysis visit window as a nominally scheduled visit, the nominally scheduled visit will be used. After applying visit window, each analysis visit should contain no more than one record and is called observed data.

**Table 8.5-1. Visit Windows for Assessments On-Treatment at Weeks 4, 8, 12**

Week/Visit	Target Day	Study Days
Week 4/Visit 4	29	2-41
Week 8/Visit 5	57	42-69
Week 12/Visit6	85	≥ 70

PASI, IGA, PGIC

##### **8.7.2.2      Handling of Dropouts or Missing Data**

Missing data will not be imputed. All analyses will be based on observed data. For all by-visit analyses of clinical endpoints, the final visit is either Week 12/Visit 6 if a subject completed the study, or the discontinuation visit.

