#### **13.2 Subject Discontinuation**

A subject may be withdrawn from the trial prior to completion for any of the following reasons:

- AEs
- Death
- Lack of efficacy
- Lost to follow-up
- Non-compliance with study drug
- Physician decision
- Pregnancy
- Progressive disease
- Protocol deviation
- Study terminated by Sponsor
- Withdrawal by subject; NOTE: if the subject decides to withdraw from the trial due to an AE then it should be classified as withdrawal due to an AE
- Other (e.g., any reason that may affect the outcome of the trial or safety of subjects)

If a subject withdraws from the trial prematurely for any reason, the site should make every effort to have the subject return to the clinic to perform all of the required visit activities and to collect and reconcile all test articles (if applicable). If the subject will not return to the clinic, the site should make every attempt to contact the subject; otherwise the subject will be considered lost to follow-up.

---

 Defined as the lack of expected or desired effect related to a therapy.

 Defined as a disease process that is increasing in extent or severity.

When a subject is withdrawn from the trial for a test article related AE (as defined in Section 14.2), when possible, the subject should be followed until resolution or stabilization of the AE. If the subject is discontinued from the trial due to pregnancy, the pregnancy and its outcome should be followed.

Subjects who are prematurely withdrawn or discontinued from the trial will not be replaced.

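### The SAP does not say whether an early leaver's exit assessment stays in its study-day window or fills the Week 12/EOT row; under windowing, leavers before Day 70 drop out of the Week 12 responder rates

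*SAP*

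**What the plan says.** **Placement by study day.** SAP 8.7.2.1 keeps scheduled assessments at their nominal visit. For exits it says: "Early termination visit will be assigned to analysis visits as defined in the visit window tables below". Table 8.5-1 sends Days 2-41 to Week 4, Days 42-69 to Week 8, and Day 70 or later to Week 12. On clashes: "If the early termination visit occurs within the same analysis visit window as a nominally scheduled visit, the nominally scheduled visit will be used". The outcome is then named: "After applying visit window, each analysis visit should contain no more than one record and is called observed data".

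**Missing data.** SAP 8.7.2.2 says: "Missing data will not be imputed. All analyses will be based on observed data". The next sentence says that, for by-visit clinical analyses, "the final visit is either Week 12/Visit 6 if a subject completed the study, or the discontinuation visit". SAP 8.7.1 carries the same sentence. Neither place says what the final visit is used for, and the SAP defines no separate final-visit row. The last row of each clinical endpoint is labelled Week 12/EOT.

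**Denominator.** For the PASI-50, PASI-75 and IGA responder proportions the SAP gives no denominator beyond the general statement on frequencies and percentages in 8.1.

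**Leavers.** Protocol 13.2 lists lack of efficacy and progressive disease among the withdrawal reasons. When a subject withdraws, "the site should make every effort to have the subject return to the clinic to perform all of the required visit activities". It adds: "Subjects who are prematurely withdrawn or discontinued from the trial will not be replaced".

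**Endpoint label.** SAP 8.7.1 attaches its primary-efficacy label to PASI change at Weeks 4, 8 and 12/EOT together. SAP 3.2 and protocol 17.2.3 list PASI change at Week 12/Day 85 only.

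**The concern.** Two programmers could follow this SAP in good faith and fill the Week 12/EOT row differently. One would leave a Day 50 exit in Week 8 and show the subject as absent at Week 12. The other would take the final-visit sentence, which sits under the dropout heading, as putting that exit in Week 12/EOT.

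If windowing governs, two consequences follow that the SAP does not spell out:

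- The Week 12 responder rates describe only subjects with a record on Day 70 or later, although treatment failure is among the listed reasons for leaving.
- The same-window rule can displace an exit assessment from every by-visit row, although the protocol asks sites to try to obtain the visit activities at exit.

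At stake is what the reported Week 12 PASI and IGA figures mean. In an open-label trial, a placement rule or denominator chosen after the data are seen would be data-dependent.

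**Working it through.** The plan has no calculated figure to reproduce: N=10 is called standard, with no power calculation (SAP 8.4, protocol 17.1). The checks below apply its rules to cases.

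**1. Where the two rules can differ.** Inputs: Table 8.5-1. Days 2-41 are 40 days and Days 42-69 are 28 days, so 40 + 28 = 68 study days on which an exit is Week 4 or Week 8 by the table but could be Week 12/EOT by the final-visit sentence. From Day 70 on, both give Week 12.

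**2. Exit assessments displaced by the same-window rule.** Inputs: Table 8.5-1 and the visit windows Day 29 ± 3 and Day 57 ± 3 (protocol 9.4, 9.5), with both visits attended before any later exit.

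Displaced days = (41 − Visit 4 day) + (69 − Visit 5 day)

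| Visit 4 / Visit 5 | Displaced exit days | Share of 68 |
|---|---|---|
| Day 29 / 57 | 12 + 12 = 24 (Days 30-41, 58-69) | 35.3% |
| Day 26 / 54 | 15 + 15 = 30 | 44.1% |
| Day 32 / 60 | 9 + 9 = 18 | 26.5% |

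These are counts of days, not probabilities. Example: Visit 5 on Day 57 and exit on Day 65. Week 8 uses Day 57, Week 12 is empty, and the Day 65 PASI is in no by-visit row.

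**3. Week 12 responder rate under windowing.** The documents give no dropout or response rate, so these counts are assumptions: 10 subjects, 3 responders among completers, and d non-responding leavers before Day 70.

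Observed-case rate = 3/(10 − d); Safety-population rate = 3/10 = 30.0%

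| d | Observed-case |
|---|---|
| 0 | 3/10 = 30.0% |
| 1 | 3/9 = 33.3% |
| 2 | 3/8 = 37.5% |
| 3 | 3/7 = 42.9% |
| 4 | 3/6 = 50.0% |

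With 2 to 5 completer responders, the gap is 2.2 to 5.6 points for one leaver, 5.0 to 12.5 for two and 8.6 to 21.4 for three. For scale, the exact 95% interval for 3/10 is 6.7% to 65.2%.

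**4. Windowing against the final-visit reading.** Assume 2 leavers before Day 70 and 4 responders among 8 completers. Windowing gives 4/8 = 50%. Counting the exit record at Week 12/EOT gives (4 + e)/10, where e is the number of leavers responding at exit: 40%, 50% or 60% for e = 0, 1, 2. The direction is not fixed.

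**5. Mean PASI change.** Assume completers average −6, so windowing gives −6.0 whatever d is. The final-visit reading gives ((10 − d)(−6) + d·m)/10, where m is the leavers' mean change. For d = 1 to 4:

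- m = +1: −5.3, −4.6, −3.9, −3.2
- m = −8: −6.2, −6.4, −6.6, −6.8

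**The case against.** **The conflict is weak.** Section 8.7.2.1 gives an explicit rule for exits and defines the result as observed data. Section 8.7.2.2 then bases everything on observed data and rules out imputation. Moving a Day 35 record to Week 12 would act like a carry-forward. EOT is simply the protocol's name for Visit 6. All of this stands, and it is why windowing is the better-supported reading. A reader might infer that the SAP plainly contradicts itself or prescribes last observation carried forward; the text supports neither. What remains is a sentence stated twice with no stated function.

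**The loss is visible.** SAP 8.1 promises subject listings and a count of non-missing values for continuous summaries, and 8.5 tabulates withdrawals with reasons. With about 10 subjects, a reader could find a displaced exit record and recompute a rate. This largely stands: exit data would be absent from by-visit summaries, not lost.

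**Exit data may not exist.** Protocol 13.2 speaks of required visit activities in general and does not name PASI, and the schedules of events are not readable in the text available. So an exit PASI is plausible, not assured.

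**Non-responder counting is a preference.** The sponsor chose observed data for a small descriptive trial, and nothing in the documents requires another rule. That is fair, and is why the observed-case rate should stay beside the alternative. But stating the denominator alone would leave leavers out of the Week 12 rate.

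**The time-point mismatch has little consequence.** A reader might infer that SAP 3.2 and the protocol designate Week 12 as primary. They list PASI change at Week 12 only and label nothing primary; the label occurs only in 8.7.1. With no hypothesis test the point is minor.

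**Conclusion.** The concern holds in a limited form and should be fixed before results are tabulated. The SAP leaves open which record fills the Week 12/EOT row for exits on Days 2-69. Its better-supported reading removes leavers before Day 70 from the Week 12 responder rates, provided the denominator is observed-case, which the SAP implies but does not state.

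The size depends on dropout, which the documents do not give. With the assumed counts above, one to three non-responding leavers raise the rate by about 2 to 21 points. With no exit before Day 70 the effect is nil. At N=10 the shift is small beside sampling error, and no type I error or power is involved.

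Two further inferences go too far. The rate is not always inflated: it does not move if no completer responds (0/7 and 0/10 are both 0%), and leavers who were responding would pull the comparison the other way. Nor is everyone who stops dosing lost: protocol 14.3 keeps subjects who meet its dosing-stopping rules in follow-up, so they may still have Week 12 data.

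**What to change.** 1. **One placement rule.** State in SAP 8.7.1 and 8.7.2.2 that Table 8.5-1 alone defines Weeks 4, 8 and 12. Use the discontinuation-visit sentence only for a separate last-observation summary, shown beside the Week 12 mean PASI change with n observed. Say that this summary keeps exit records displaced by the same-window rule.
2. **Responder rates.** For PASI-50, PASI-75 and the IGA responder categories, report the rate with the Safety population as denominator and missing counted as non-response, beside the observed-case rate with its n. Amend the no-imputation sentence in 8.7.2.2 to allow this.
3. **Minor.** In 8.7.1, attach the primary label to PASI change at Week 12 and call Weeks 4 and 8 supportive. Editorially, add BSA to the footnote of Table 8.5-1, since 8.7.1 also analyses BSA at these visits.

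The cost is SAP wording, one last-observation table and one extra responder presentation per endpoint, with no new data. The headline responder rate may be lower, and it understates response if leavers were responding: in the two-leaver example it is 4/10 = 40%, against 60% had both been responding at exit. Responder rates and mean change would also treat missing data differently; the last-observation summary makes that visible.

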##### **8.7.2.3      Interim Analyses**

No interim analysis is planned.

##### **8.7.2.4      Multicenter Studies**

All study sites adhered to the same protocol and will have their data pooled for summary purposes.

##### **8.7.2.5      Multiple Comparisons / Multiplicity**

None

##### **8.7.2.6      Examination of Subgroups**

None

## **8.8 Safety Evaluation**

### ***8.8.1 Extent of Exposure***

Descriptive statistics will be used to summarize the extent of exposure in the Safety population. The total number of doses taken will be assessed by tablet counts. The frequency and percentage of exposure extent will be summarized based on the following categories: < 4 weeks,  $\geq$  4 weeks,  $\geq$  8 weeks, and  $\geq$  12 weeks.

### ***8.8.2 ADX-629 Metabolite Analysis***

Urine and plasma drug metabolite(s) at Day 29 will be analyzed in a separate report by the vendor to be appended to the Clinical Study Report.

### ***8.8.3 Adverse Events***

All AEs reported during the study will be listed, documenting course, severity, investigator assessment of the relationship to the test articles, and outcome. Verbatim terms will be coded to preferred terms (PTs) and system organ class (SOC) using version 24.0 of the Medical Dictionary for Regulatory Activities mapping system. The PTs and SOC will then be tabulated. For all AE summaries, if a subject has more than one AE within a PT, the subject is counted once in that PT. If a subject has more than one AE within a SOC, the subject is similarly counted once in that SOC.

The number and percentage of unique subjects reporting each treatment emergent AE (TEAE) will be summarized by SOC and PT. The number and percent of unique subjects reporting each TEAE will also be summarized by SOC, PT, and maximum severity (mild, moderate, severe) and closest relationship to test article (not related, unlikely related, possibly related, probably related, and definitely related).

Serious AEs, if any, will be summarized by SOC, PT and treatment group.

### ***8.8.4 Physical Examinations***

Physical examination results will be included in medical history listings (from Screening and Baseline) or AE summaries and listings if new or clinically significant worsening abnormalities were observed at post-Baseline physical examinations.

### ***8.8.5 Vital Signs***

Descriptive statistics will be provided for the observed and change from Baseline values for temperature, systolic and diastolic blood pressure, heart rate, and respiration rate at Week 4, 8, and 12/EOT. A subject data listing will also be provided.

### ***8.8.6 Electrocardiograms***

Descriptive statistics will be provided for the observed and change from Baseline values for ECG parameters (heart rate, PR interval, QRS duration, QT interval, P axis). Changes in overall

cardiologist interpretation of the ECG (Normal, Abnormal Not Clinically Significant, Abnormal Clinically Significant) from Baseline to Week 4, 8, and 12/EOT will be summarized by shift table. A subject data listing will also be provided of the data above, including listing any findings and the investigator's determination of clinical significance.

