**17.3.1.4 Electrocardiograms**

ECGs will be evaluated for any material changes during the trial period. Descriptive statistics of ECG parameters will be provided. Changes in overall interpretation of the ECG from Baseline to Days 29, 57, and 85/EOT will be examined using shift tables.

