## 2. PURPOSE OF THE ANALYSES

The purpose of this SAP is to outline the planned analyses to be completed to support the Clinical Study Report (CSR) for Protocol ADX-629-PS-001. Any post-hoc or unplanned analyses not identified in this SAP will be clearly identified in the CSR.

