### 3.3 Safety Endpoints

1. Incidence (severity and causality) of any local and systemic adverse events (AEs)
2. Changes from Baseline in vital signs at Week 4, 8, and 12/EOT
3. Changes from Baseline in clinical laboratory tests (chemistry, hematology, and urinalysis) at Week 4, 8, and 12/EOT
4. Changes from Baseline in overall interpretation of the electrocardiogram (ECG) at Week 4, 8, and 12/EOT

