## 7.3 Electrocardiogram

12-lead ECGs will be performed at every clinic visit after the subject has rested for at least 10 minutes in the supine positions. Heart rate, PR interval, QRS duration, QT interval, P axis will be measured. Any ECG machine findings will be recorded. The cardiologist will review as normal, abnormal not clinically significant, or abnormal clinically significant. And the investigator will assess if the results are clinically significant (yes or no).

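### The planned ECG table summarises change from Baseline in uncorrected QT only, so its QT row mixes heart-rate change with repolarisation change

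*SAP*

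**What the plan says.** SAP 7.3 defines what is taken from each 12-lead ECG: "Heart rate, PR interval, QRS duration, QT interval, P axis will be measured". SAP 8.8.6 carries the same five items into the analysis: "Descriptive statistics will be provided for the observed and change from Baseline values for ECG parameters", with the list repeated in parentheses: "ECG parameters (heart rate, PR interval, QRS duration, QT interval, P axis". The protocol is less specific; section 17.3.1.4 says only "Descriptive statistics of ECG parameters will be provided". No readable part of either document, including both abbreviation lists, mentions QTc, Fridericia, Bazett or any other rate correction, and SAP section 9 records no change to the planned analysis.

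The ECG safety endpoint is a different quantity. SAP 3.3 states it as "Changes from Baseline in overall interpretation of the electrocardiogram (ECG) at Week 4, 8, and 12/EOT", and 8.8.6 analyses it with a shift table of the cardiologist's three-category reading. For individuals, 8.8.6 adds "A subject data listing will also be provided of the data above", together with ECG findings and the investigator's judgement of clinical significance.

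On anything added later, SAP section 2 says "Any post-hoc or unplanned analyses not identified in this SAP will be clearly identified in the CSR"; SAP 8.3 repeats the commitment.

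**The concern.** QT depends on heart rate, so a change in raw QT between Baseline and Week 4, 8 or 12 has two sources: a change in repolarisation and a change in rate. In a randomised trial a control arm would absorb rate drift between visits. This trial has one open-label arm, so nothing does.

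The heart-rate row in the same table is only a partial remedy. Two separate summary rows do not show which subject's QT change went with which heart-rate change, so a reader cannot recover per-subject corrected changes, or their spread, from the table.

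What is at stake is the interpretability of the only numerical summary of repolarisation planned in a trial whose sample-size section gives safety and tolerability as its main purpose. The row can hide a real lengthening or show one that is only slowing of the heart. If a corrected QT is calculated after the data are seen, the formula becomes a post-hoc choice.

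**Working it through.** **Plan's own figure.** There is none to reproduce. Neither document gives a QT, a heart rate, an expected change or a threshold. Everything below is an illustration on assumed values.

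**Assumptions.** Baseline heart rate (HR) 60, 70 or 80 bpm; Baseline Fridericia-corrected QT (QTcF) 380 to 440 ms.

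**Formulas.** QTcF = QT / (60/HR)^(1/3), so QT = QTcF × (60/HR)^(1/3). Bazett uses the exponent 1/2.

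**1. Masking: raw QT unchanged, HR rises.** The hidden QTcF increase is QTcF × [((HR + d)/HR)^(1/3) − 1]. The smallest value is at HR 80, QTcF 380 and the largest at HR 60, QTcF 440.

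| HR rise d | Smallest | Largest |
|---|---|---|
| 5 bpm | +7.8 ms | +11.9 ms |
| 10 bpm | +15.2 ms | +23.2 ms |

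**2. False signal: QTcF unchanged, HR falls.** The apparent raw QT change is QTcF × [(60/(HR − d))^(1/3) − (60/HR)^(1/3)].

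| HR fall d | Smallest | Largest |
|---|---|---|
| 5 bpm | +7.5 ms | +12.9 ms |
| 10 bpm | +15.7 ms | +27.6 ms |

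**3. Mid-range case.** HR 70 and QTcF 400 give raw QT = 400 × (60/70)^(1/3) = 380.0 ms.
- Raw QT still 380.0 at HR 80: QTcF = 418.2, a hidden rise of 18.2 ms.
- QTcF still 400 at HR 80: raw QT = 363.4, an apparent fall of 16.5 ms.
- QTcF still 400 at HR 60: raw QT = 400.0, an apparent rise of 20.0 ms.
- True QTcF rise of 10 ms (400 to 410) with HR 70 to 75: raw QT = 410 × (60/75)^(1/3) = 380.6, so the planned row shows +0.6 ms.
- The same true rise with HR falling to 65: raw QT = 399.2, so the planned row shows +19.2 ms.

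**4. Pairing.** Suppose five of ten subjects go from 70 to 80 bpm and five from 70 to 60 bpm, all at constant QTcF 400. The mean HR change is 0. The raw QT changes are five of −16.5 and five of +20.0 ms: mean +1.7 ms, SD 19.3 ms. The QTcF changes are all 0. The mean is barely moved; the spread and the individual values come entirely from heart rate.

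**5. Choice of formula.**
- At the edge of the grid, raw QT 440 ms unchanged and HR 60 to 70: Fridericia 440 × (70/60)^(1/3) = 463.2 (+23.2 ms); Bazett 440 × (70/60)^(1/2) = 475.3 (+35.3 ms).
- In the middle, raw QT 380 ms unchanged and HR 70 to 80: +18.2 ms by Fridericia and +28.3 ms by Bazett.

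In both cases the formula alone changes the answer by 10 ms or more, which is why it should be fixed in advance.

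**The case against.** The best case on the other side is that little depends on this row. The table is descriptive, with no test and no QT threshold, and the named endpoint is the shift in overall interpretation. Each ECG is read by a cardiologist and assessed by the investigator. With about ten subjects and three post-Baseline visits there are roughly 30 post-Baseline ECGs, all listed with QT and heart rate, so anyone can compute a corrected value. A systematic heart-rate shift would show in the heart-rate row and again under vital signs. ECGs follow at least 10 minutes of supine rest, which limits rate variation. Nothing in the documents suggests that ADX-629 changes heart rate or QT.

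Much of this stands, and it keeps the point small. The group mean is also less exposed than individual values. In a simulation of ten subjects (Baseline HR 70, SD 8; HR change +5, SD 8; constant QTcF 410, SD 18), the rate-driven part of the mean QT change could be recovered from the mean heart rates to within about 2 ms in 95% of trials.

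That recovery is itself a rate correction, however, and the plan does not include one. It also does nothing for the SD, minimum and maximum that the table will print. The documents do not say whether the cardiologist's reading takes heart rate into account, and a three-category reading gives no magnitude. Labelling a later analysis as unplanned is honest, but it does not remove the post-hoc choice of formula. The schedules of events and the eCRF could not be seen. A QTc field there would not change what 8.8.6 says will be tabulated.

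**Conclusion.** The concern holds. Followed exactly, SAP 8.8.6 produces a QT change row that cannot separate repolarisation from heart rate. For heart-rate changes of 5 to 10 bpm the distortion is about 8 to 28 ms in an individual, in either direction. That range rests on assumed Baseline heart rates of 60–80 bpm, assumed QTcF of 380–440 ms and the Fridericia relation; none of these values comes from the documents.

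This is a pre-specification gap in a supporting safety table. It does not affect the ECG endpoint, a formal conclusion or the data collected. A corrected QT would remove rate dependence only; it would not address the small sample or ECGs that are not timed to dose. The change should be made because the QT row is the only planned number on repolarisation and the remedy costs almost nothing.

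**What to change.** Before database lock, amend SAP 7.3 and 8.8.6 as follows:

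- Name one correction and derive it for every ECG from the QT and heart rate of that same ECG, for example QTcF = QT / (60/HR)^(1/3), with QT in ms and HR in bpm.
- Add observed and change-from-Baseline QTcF at Weeks 4, 8 and 12/EOT to the ECG parameter table. Raw QT can stay.
- Add each subject's maximum post-Baseline QTcF and largest increase from Baseline to the listing. This goes a little beyond repairing the row, but with about ten subjects the individual values are what a reader will look at.

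The cost is one derived variable, one added set of table rows and two listing columns. No new measurement is needed.
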